14.3.5 Other effect measures

14.3.5.1 Neurological exam

Although not used for determining response, it is useful to evaluate changes in the neurological exam compared to the previous exam. The following scale may be used:

+2	Definitely better
+1	Possibly better
0	Unchanged
-1	Possibly worse
-2	Definitely worse

14.3.5.2 Performance status

Participants will be graded according to KPS score

14.3.5.3 Overall survival time

From date of first dose (date of first post-surgery treatment for participants in Dose Level 1) to date of death due to any cause.

14.3.5.4 Progression-free survival time:

From date of first dose (date of first post-surgery treatment for participants in Dose Level 1) to date of progression or death. Participants who stop treatment for causes other than progression may be censored if other therapy is initiated or if regular assessments for assessing progression are no longer available.

14.4 Appendix 4: Cockcroft-Gault formula

Female:

$$GFR[ml / min] = 0.85 \cdot \frac{(140 - age[y]) \cdot bodyweight[kg]}{72 \cdot serum\ creatinine [mg / dl]}$$

Male:

$$GFR[ml / min] = \frac{(140 - age[y]) \cdot bodyweight[kg]}{72 \cdot serum\ creatinine [mg / dl]}$$

**Document History – Changes compared to previous version of RAP module 3.**

Version	Date	Changes
Draft 1.0	05-Aug-2015	Original version
Amendment 1.0	11-Mar-2019	
Section 1:
 

Standard languages added to clarify that the SAP should be finalized before database lock

 
Section 1.1:
 

Details added describing the study design with regards to each study arm

Timeline for primary and final analysis updated to align with protocol amendment 6

 
Section 1.2:
 

Details added for the definition of primary endpoint in Section 1.2.1

Details and clarification added for other secondary objectives for endpoints and study arms in Section 1.2.2

 
Section 2.1:
 

Study arms used with regard to the general presentation of descriptive summaries updated

Subgroup analysis removed

 
Section 2.2:
 

Per-protocol set was removed

[REDACTED]

 
Section 2.3:
 

By prior radiation to the brain and by prior ALK inhibitor use analyses removed

Details of summaries of diagnosis and extent of cancer, medical history, and prior anti-cancer therapy were updated to align with eCRF

 
Section 2.4:
 

Summary of major protocol deviations leading to exclusion from PPS removed

 
Section 2.5:
 

By prior radiation to the brain and by prior ALK inhibitor use analyses removed

Details of summaries of disposition were updated to align with eCRF

 
Section 2.6:

---

Version	Date	Changes
		

• Baseline definitions for general efficacy and safety evaluations moved from Section 2.8.2

• Exposure by prior radiation to the brain and by prior ALK inhibitor use analyses removed

• Kaplan-Meier analysis for dose reduction or interruption removed

		Section 2.7: 

• Definition and derivation algorithm of best overall response moved from Section 2.8.1.2 to Section 2.7.1. The cut-off for SD too early and PD too late was updated based on tumor assessment schedule.

• Subgroup analysis and PPS analysis were removed from Section 2.7.4

		Section 2.8: 

• Description of secondary efficacy endpoints moved from Section 2.8.1 to Section 2.8.1.2

• Table 2-1 updated to remove supportive analysis and subgroup analysis. IDCR and EDCR at week 8 and week 16 added.

• PPS analysis and subgroup analysis removed from Section 2.8.1.1

• OIRR, TTIR and DOIR analyses based on all patients added in Section 2.8.1.2

• IDCR and EDCR at week 24 updated to at week 8 and week 16. Algorithms on derivation of IDCR and EDCR at 8 and 16 weeks added. Similar analyses based on patients with measurable brain metastases added for IDCR in Section 2.8.1.2

• Methods used for TTIR, TTER and TTR analyses changed from KM method to descriptive summary in Section 2.8.1.2

• The strategy of handling start of new anticancer therapy updated from censoring to the new standard of ignoring for DOIR, DOER, DOR and PFS analyses in Section 2.8.1.2.

• Supportive and PPS analyses for ORR and DCR per BIRC removed in Section 2.8.1.2

• Gap analyses removed from Section 2.8.1.2

• On treatment deaths, by primary SOC and PT, AESI leading to study drug discontinuation, two safety disclosure tables added and subgroup analysis for AEs removed in Section 2.8.2

---

---

Version	Date	Changes
		

• Lab parameter updated to include RBC and direct bilirubin; Urinalysis listings were removed; Categories for liver function tests updated in Section 2.8.2

• The denominator used for the percentage calculation for ECG abnormality was further clarified; respiration rate removed from vital sign analysis; Clarification for the analysis of WHO PS added in Section 2.8.2.1

• [REDACTED]

• [REDACTED]

• Sample size calculation and power analysis updated to align with protocol amendment in Section 2.9 and Section 2.10

• A preliminary interim analysis for arm 5 added in Section 2.11

		Section 3: 

• Table 3 added to include the changes to protocol specified analyses

		Section 4: 

• Patient classification into analysis sets removed

• Further details were added for the derivation of last contact date in Section 4.2

• Age derivation added as Section 4.4

• “New anticancer therapy will defined for whole body, intracranial, and extracranial separately” added; PFS censoring reasons updated in Section 4.6.1.

• Details of PROC LIFETEST added in Section 4.6.4

• Baseline ECG definition updated in Section 4.7

• Imputation rule for death date updated in Section 4.8.6

• Imputation rule for concomitant medication date added as Section 4.8.2 and imputation incomplete dates for disease progression prior to start of study drug added as Section 4.8.8

---

4.3	Month derivation .....	39
4.4	Age derivation .....	39
4.5	Dose interruptions and dose changes.....	39
4.6	Efficacy endpoints .....	40
4.6.1	Implementation of RECIST guidelines.....	40
4.6.2	Implementation of RANO guidelines (protocol Appendix 3).....	44
4.6.3	Sources for overall lesion response.....	46
4.6.4	Kaplan-Meier estimates .....	47
4.6.5	Confidence interval for response rates.....	47
4.7	Safety evaluations.....	48
4.7.1	Multiple assessments within post-baseline visits.....	48
4.7.2	Baseline .....	48
4.7.3	Laboratory Parameters .....	49
4.8	Handling of missing or partial dates.....	50
4.8.1	AE date imputation .....	50
4.8.2	Concomitant medication date imputation .....	52
4.8.3	Incomplete date of initial diagnosis of cancer, date of first recurrence/progression and date of most recent recurrence.....	52
4.8.4	Incomplete date for anti-neoplastic therapies .....	53
4.8.5	Incomplete assessment dates for tumor assessment.....	53
4.8.6	Incomplete date for death.....	54
4.8.7	Incomplete dates for last dose of study drug.....	54
4.8.8	Incomplete dates for disease progression prior to start of study drug... [REDACTED]	55
5	Reference:.....	55

## 1 Introduction

This Statistical Analysis Plan (SAP) describes the planned statistical methods for all safety, efficacy, [REDACTED], [REDACTED] analyses for study LDK378A2205 final clinical study report.

The content of this SAP is based on [LDK378A2205](#) study protocol [Amendment 6](#). All decisions regarding final analysis, as defined in the SAP document, have been made prior to database lock of the study data.

### 1.1 Study design

This is a phase II, multi-center, open-label, five-arm study in which the efficacy and safety of oral ceritinib treatment will be assessed in patients with NSCLC metastatic to the brain and/or to leptomeninges harboring an ALK rearrangement using the FDA approved Vysis ALK Break Apart FISH Probe Kit (Abbott Molecular Inc.) test and scoring algorithm (including positivity criteria). The study will enroll approximately 160 patients globally.

Patients with ALK-positive NSCLC and active metastases to the brain and/or to leptomeninges will be included in this study. Patients without evidence of leptomeningeal carcinomatosis (LC) will be allocated into 1 of the 4 arms taking into account the patient's history of prior therapy: prior radiation therapy (whole brain or stereotactic radiation therapy) to the brain (yes/no) and prior treatment with an ALK inhibitor (ALKi) (yes/no) ([Table 1-1](#)). The allocation of patients into the five study arms are described below.

**Table 1-1 Allocation into Study Arms based on prior radiation to brain (yes/no) and prior treatment with ALK inhibitor (yes/no)**

	Prior Radiation to the brain: YES	Prior Radiation to the brain: NO
Prior treatment with a ALKi  : YES	Arm 1	Arm 2
Prior treatment with a ALKi: NO	Arm 3	Arm 4
Leptomeningeal disease 	Arm 5	

Previous treatment with ALK inhibitors other than crizotinib is not allowed in Arms 1, 2 and 5.

The description of patients in each of the five study arms is as follows:

- Arm 1 will include patients with metastases in the brain without evidence of leptomeningeal carcinomatosis, previously treated with radiation to the brain and with prior exposure to an ALKi.
- Arm 2 will include patients with metastases in the brain without evidence of leptomeningeal carcinomatosis, previously untreated with radiation to the brain but with prior exposure to an ALKi.
- Arm 3 will include patients with metastases in the brain without evidence of leptomeningeal carcinomatosis, previously treated with radiation to the brain but with no prior exposure to an ALKi.
- Arm 4 will include patients with metastases in the brain without evidence of leptomeningeal carcinomatosis, previously untreated with radiation to the brain and with no prior exposure to an ALKi.

- Arm 5 will include any patients with leptomeningeal carcinomatosis with or without evidence of active lesion at the baseline Gadolinium-enhanced brain MRI.

All patients will receive the same treatment regimen regardless of the arm to which they are allocated. Treatment with ceritinib will continue until the patient experiences disease progression (in the brain, outside of the brain or both) as determined by the investigator according to RECIST 1.1, unacceptable toxicity that precludes further treatment, pregnancy, start of a new anticancer therapy, discontinues treatment at the discretion of the patient or investigator, lost to follow-up, death, or study is terminated by the Sponsor.

Tumor response will be evaluated starting from the first day of treatment with ceritinib until the time of disease progression according to RECIST 1.1 as determined by investigator, withdrawal of consent for further follow-up, loss to follow-up or death. This schedule of tumor assessments must continue regardless of dose interruptions. In patients who discontinue treatment in the absence of progression, tumor assessments will continue every 8 weeks until progression of disease, withdrawal of consent for further follow-up, loss to follow-up or death.

Primary analysis of any of the study arms or overall will occur only after enrollment in the specific study arms or overall is complete and all patients have completed at least 24 weeks of treatment with ceritinib or have discontinued earlier respectively. The study will end when both of the following conditions are met:

1. At least 24 weeks after last patient treated in the study.
2. At least 75% of patients have died, have been lost to follow-up, or have withdrawn consent for survival follow-up, **or** the last patient will be able to enter into a separate rollover study and/or other options for continued treatment, whichever comes first.

If the end of study criteria is met before the primary analysis is conducted, a single final analysis and study report may be performed. If the end of the study criteria is not met by the time that the primary analysis is conducted, a final CSR will be produced reporting all available data collected up to last patient last visit (LPLV) including the additional study data collected after the primary analysis.

## **1.2 Objectives**

### **1.2.1 Primary objective**

The primary objective is to evaluate the antitumor activity of ceritinib in patients with ALK-positive NSCLC metastatic to the brain and/or to leptomeninges based on investigator assessment per RECIST 1.1. The primary endpoint is the overall response rate (ORR) defined as the proportion of patients with a best overall confirmed response of complete response (CR) or partial response (PR) in the whole body as assessed per RECIST 1.1 by the investigator.

### **1.2.2 Key secondary and other secondary objectives**

The key secondary objective is to evaluate Disease Control Rate (DCR) in patients with ALK-positive NSCLC metastatic to the brain and/or to leptomeninges based on investigator assessment per RECIST 1.1. The DCR is defined as the proportion of patients with a best overall response of CR, PR or SD in the whole body, as assessed by the investigator per RECIST 1.1.

Other secondary objectives are:

- To evaluate intracranial tumor-response related endpoints (OIRR, IDCR, TTIR and DOIR) as assessed by investigators and Blinded Independent Review Committee (BIRC) (using modified RECIST 1.1 criteria)
- To evaluate extracranial tumor-response related endpoints (OERR, EDCR, TTER and DOER) as assessed by investigators and BIRC (using RECIST 1.1 criteria)
- To evaluate whole body tumor-response related endpoints as assessed by investigators (TTR, DOR and PFS) and BIRC (ORR, DCR, TTR, DOR and PFS) (using RECIST 1.1 criteria)
- To evaluate overall survival (OS) in patients with ALK-positive NSCLC metastatic to the brain and/or to leptomeninges
- To evaluate safety in patients with ALK-positive NSCLC metastatic to the brain and/or to leptomeninges

### 1.2.3 Exploratory objectives

- To evaluate intracranial endpoints for patients with measurable brain metastases at baseline in Arms 1 to 4 (OIRR, TTIR and DOIR) and for patients with active brain lesions at baseline in Arms 1 to 4 (IDCR) using the Response Assessment in Neuro-Oncology (RANO) criteria for high grade gliomas (Wen et al 2010) by investigators and BIRC.

## 2 Statistical methods

This section and its subsections will be imported to [Section 9.7](#) of the CSR after the analyses have been conducted.

The text will be changed to the past tense when imported into the CSR; references to [Section 4](#) of the RAP, where additional details are provided for programming implementation, may be removed in the CSR.

In what follows, study drug refers to LDK378 (certinib).

## 2.1 Data analysis

Data will be analyzed by Novartis Oncology Biostatistics and Statistical Programming personnel according to the data analysis [Section 10](#) of the LDK378A2205 protocol, which will be available in [Appendix 16.1.1](#) of the Clinical Study Report (CSR). Important information is given in the following sections and details are provided, as applicable, in [Section 4](#) from which [Appendix 16.1.9](#) of the CSR will be extracted.

SAS® version 9.4 (or later version if available at time of database lock) will be used in all analyses.

Data from all patients who signed main informed consent in centers that participate in this study will be used in the analysis. Data collected after withdrawal of informed consent will not be reported. Due to expected small size of enrollment at individual centers, no center effect will be assessed. Each analysis will use all data in the database up to the analysis cutoff date, determined prior to database lock. Data collected after patients' withdrawal of informed consent for further participation in the study will not be reported (except for death date, which might be obtained from public records).

[Section 4.1](#) provides further details regarding data to be included in the analyses.

### General presentation of descriptive summaries

Qualitative data (e.g., gender, race) will be summarized by frequency counts and percentages. Percentages will be calculated using the number of patients in the relevant population or subgroup, as the denominator.

Continuous data (e.g., age, body weight) will be summarized by appropriate descriptive statistics (i.e. mean, standard deviation, median, minimum, and maximum).

All baseline characteristics, efficacy (except intracranial endpoints by RANO) and safety analyses will be presented by study arm (Arm 1, Arm 2, Arm 3, Arm 4 and Arm 5) and for all patients.

In addition, all efficacy endpoints, except intracranial endpoints by RANO, will be presented by prior radiation to the brain (Arms 1+3 vs. Arms 2+4) and by prior ALK inhibitor use (Arms 1+2 vs. Arms 3+4) and overall, for patients from Arms 1 through 4, unless otherwise specified. Intracranial endpoints by RANO will be presented by study arm for patients in Arm 1 to Arm 4 and overall, for patients from Arms 1 through 4.

## 2.2 Analysis sets

A patient is considered to be enrolled into the study if they have signed a study informed consent. Only patients who have signed a study informed consent will be included in the analysis data sets.

### Full Analysis Set

The Full Analysis Set (FAS) consists of all patients who received at least one dose of study drug.

[figure not shown]
The FAS will be used for summaries of baseline characteristics and all efficacy analyses, unless otherwise specified.

The following endpoints will be analyzed on a subset of FAS:

Patients with measurable brain metastases: Overall intracranial response rate (OIRR), Time to intracranial tumor response (TTIR) and Duration of intracranial response (DOIR)

### **Safety Set**

The Safety Set consists of all patients who received at least one dose of study drug. All safety data will be analyzed using the Safety Set. The FAS and Safety Set in this study are identical.

### **2.3 Patient demographics and other baseline characteristics**

The FAS will be used for all patient demographic and baseline characteristic summaries and listings, unless otherwise specified. Summaries will be produced by study arm and for all patients. Listings will be produced by study arm.

## Basic demographic and background data

All demographic and baseline disease characteristics data will be summarized by study arm and for all patients. Categorical data (e.g. gender, race, ethnicity, WHO performance status, age groups: <65, 65-<85, ≥85 years, smoking history) will be summarized by frequency count and percentages. Continuous data (e.g. age, weight, height) will be summarized by descriptive statistics (as defined in [Section 2.1](#)).

## Diagnosis and extent of cancer

Descriptive statistics and frequency counts and percentages will be tabulated by study arm, as appropriate, for diagnosis and extent of cancer based on the data collected on the electronic Case Report Form (eCRF) including primary site of cancer, predominant histology/cytology, histological grade, time (in months) from initial diagnosis of primary site, stage at initial diagnosis, stage at time of study entry, time (in months) from initial diagnosis to first recurrence/progression, time (in months) from most recent relapse/progression, metastatic sites of cancer, number of metastatic sites of cancer, types of intracranial and extracranial lesions (target and non-target lesions) at baseline based on investigator and BIRC assessment, Intracranial lesion (target and non-target) location at baseline, disease burden (intracranial, extracranial and whole body) at baseline for target lesion based on investigator and BIRC (based on the data collected on the RECIST eCRF page).

## Medical history

Medical history and ongoing conditions, including cancer-related conditions and symptoms, will be summarized and listed by study arm. Separate summaries will be presented for ongoing and historical medical conditions. The summaries will be presented by primary system organ class and preferred term, in each study arm and all patients. Medical history and current medical conditions are coded using the Medical Dictionary for Regulatory Activities (MedDRA) terminology.

## Prior anti-cancer therapy

Prior anti-neoplastic (anti-cancer) therapy will be listed in three separate categories: 1. medications, 2. radiotherapy, and 3. surgery.

The number and percentage of patients who received any prior anti-neoplastic medications, prior antineoplastic therapy Crizotinib, prior anti-neoplastic radiotherapy, prior anti-neoplastic radiotherapy to the brain, or prior anti-neoplastic surgery will be summarized by study arm and for all patients.

Prior anti-neoplastic medications will be summarized by study arm. Summaries will include chemotherapy (medication) setting, other therapy (medication) setting, number of prior regimens (crizotinib and other), therapy type, setting, best response at last treatment, time from last treatment start to progression and duration of last treatment best response. Prior antineoplastic medications will also be summarized by ATC class, preferred term and study arm. Prior antineoplastic therapy crizotinib will be summarized by study arm and includes setting, best response at last crizotinib treatment, time from last crizotinib treatment start to progression, duration of last crizotinib treatment best response and reason for discontinuation of last crizotinib treatment.

For radiotherapy and radiotherapy to the brain, time since last radiotherapy end to treatment start, locations, setting and method of last therapy will be summarized. For prior surgery, time since last surgery, procedure and residual disease at last surgery will be summarized. ATC class and preferred term will also summarize steroid use at the start of study drug.

## Screening phase disposition

A patient who signs study informed consent but fails to satisfy all of the eligibility criteria for any reason will be considered a screen failure. These patients are not treated with study drug. Frequency counts and percentages will be tabulated for all enrolled patients as follows:

- Number (%) of patients who completed screening phase (based on the presence of study phase completion date and the 'Next phase entered' is 'Treatment' in the 'Screening Phase Disposition' page);
- Number (%) of patients who discontinued during screening phase (based on the presence of date of discontinuation and discontinuation / "subject status" reason entered and 'Will the subject continue into the next phase of the trial' is 'No' in the 'Screening Phase Disposition' page);
- Reasons for screening phase discontinuation (based on reasons recorded in Screening Phase Disposition' page).

All screen failure patients with reasons for screen failure will be listed.

## 2.4 Protocol deviations

Frequency counts and percentages of patients in the FAS with any CSR reportable protocol deviations (related to study inclusion/exclusion criteria, conduct of the trial, patient management or patient assessment) will be tabulated by the deviation category by study arm and for all patients.

All protocol deviations will be listed.

## 2.5 Patient disposition

The FAS will be used for the patient disposition summary tables and listings. The following will be tabulated by study arm.

Related to the treatment phase:

- Number (%) of patients who are still on-treatment (based on the absence of the 'End of Treatment Disposition' page);
- Number (%) of patients who discontinued treatment (based on completion of the 'End of Treatment Disposition' page with date of discontinuation and reason of discontinuation/ 'Subject Status' entered);
- Number (%) of patients who entered post treatment follow-up phase from treatment phase (based on 'Next Phase Entered' is 'Post-treatment follow-up' on the 'End of Treatment Disposition' page for patients who discontinued treatment);
- Number (%) of patients who entered survival follow-up from treatment phase (based on 'Will the subject be followed for survival' is 'Yes' on the 'End of Treatment Disposition' page for patients who discontinued treatment);

CONFIDENTIAL - For Business Use Only

- Number (%) of patients who discontinued from study from treatment phase (based on ‘Will subject continue into the next phase of the trial’ is ‘No’ as entered on the ‘End of Treatment Disposition’ page for patients who discontinued treatment);
- Primary reasons for study treatment discontinuation (based on discontinuation reasons entered under ‘Subject Status’ in the ‘End of Treatment Phase Disposition’ page).

Related to the post-treatment follow-up phase:

- Number (%) of patients who are still in the post-treatment follow-up phase (based on presence of ‘End of Treatment Disposition’ and absence of ‘End of Post Treatment Phase Disposition’ page);
- Number (%) of patients who discontinued from the post-treatment follow-up (based on completion of ‘End of Post Treatment Phase Disposition’ page with date of discontinuation and discontinuation reasons entered under ‘Subject Status’);
- Number (%) of patients who entered survival follow-up (based on completion of ‘End of Post Treatment Phase Disposition’ page with date of discontinuation and discontinuation reasons entered under ‘Subject Status’ and ‘Will the subject be followed for survival’ is ‘Yes’ for patients who discontinued from the post-treatment follow-up);
- Number (%) of patients who discontinued from study (based on completion of ‘End of Post Treatment Phase Disposition’ page with date of discontinuation and discontinuation reasons entered under ‘Subject Status’ and ‘Will subject be followed for survival’ is ‘No’ for patients who discontinued from the post-treatment follow-up);
- Primary reasons for discontinuation from the post-treatment follow-up (based on discontinuation reasons entered under ‘Subject Status’ in the ‘End of Post Treatment Phase Disposition’ page).

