7.1.6.2 Post-treatment follow-up

All patients who discontinued treatment during the treatment phase for reasons other than death, lost to follow-up, pregnancy or disease progression as per investigator assessment ([Section 7.1.3](#)) will continue tumor assessments as per [Table 7-1](#) (every 8 weeks) thereafter until PD as per investigator assessment, withdrawal of consent or death. Once the patient ceases tumor follow-up, the reason for completion should be recorded on the End of Post Treatment Disposition (Study Phase Completion) eCRF page.

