7.1.6.3 Survival follow-up

All patients who had PD as per investigator assessment, have started a new anti-neoplastic therapy, and/or withdrew consent from further study assessments will subsequently be followed for survival information every 12 weeks until death, lost to follow-up or withdrawal of consent for survival follow-up. The investigator or his designee will collect this survival

information and any new anti-neoplastic therapies for all patients until the final survival analysis.

Follow-up can be done via a phone contact. Antineoplastic therapies will be captured on the 'Antineoplastic therapies since discontinuation of study treatment' eCRF page following the last dose of the study treatment.

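### The SAP's disposition row for patients still in post-treatment follow-up also counts discontinued patients who never entered that phase

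*SAP*

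**What the plan says.** SAP 2.5 builds the disposition table from two eCRF pages. The row for patients still in post-treatment follow-up has two conditions and no others: "Number (%) of patients who are still in the post-treatment follow-up phase (based on presence of ‘End of Treatment Disposition’ and absence of" the End of Post Treatment page.

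The treatment-phase part of the same table has three rows for where a patient goes on stopping ceritinib:

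- into tumour follow-up: "Number (%) of patients who entered post treatment follow-up phase from treatment phase (based on 'Next Phase Entered' is 'Post-treatment follow-up' on the" End of Treatment page;
- directly to survival follow-up: "Number (%) of patients who entered survival follow-up from treatment phase (based on 'Will the subject be followed for survival' is 'Yes' on the" same page;
- directly out of the study: "Number (%) of patients who discontinued from study from treatment phase", again read from that page.

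Protocol 7.1.6.2 continues tumour assessments after treatment only for patients who did not stop because of death, loss to follow-up, pregnancy or investigator-assessed progression. On the second page it says: "Once the patient ceases tumor follow-up, the reason for completion should be recorded on the End of Post Treatment Disposition" page. Protocol 7.1.6.3 assigns progressed patients to survival follow-up, in a sentence that begins "All patients who had PD as per investigator assessment, have started a new anti-neoplastic therapy".

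**The concern.** The SAP recognises that some patients go from treatment straight to survival follow-up or out of the study. It also has the field that identifies those who entered tumour follow-up. Yet it does not carry that field into the row for patients still in the phase, so absence of the second page stands for two different things: the phase is continuing, or it was never entered.

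At stake is the credibility of the disposition table. It would show patients who have died, progressed or left as being under active tumour follow-up, and the post-treatment rows would not reconcile with the number who entered the phase.

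**Working it through.** The plan states no figure to reproduce. The check applies the rule to each route that the documents allow.

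**Inputs**

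- Rule for the row, and the entry field: SAP 2.5.
- Who enters tumour follow-up: Protocol 7.1.6.2. Table 7-1 likewise heads that column as being for patients without PD at end of treatment.
- First page: completed when ceritinib stops, with the reason; death is a listed stopping reason (Protocol 7.1.4.1). SAP 2.5 treats absence of this page as still on treatment, so a patient who died on treatment must have one.
- Second page: completed by patients who continue assessments after treatment, when those assessments end (Protocol 7.1.4.1 and 7.1.6.2).

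**Step 1. Rule applied by route**

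| Route | First page | Second page | Counted as still in? | Truly still in? | Counted with entry condition added? |
|---|---|---|---|---|---|
| On treatment | no | no | no | no | no |
| Died on treatment | yes | no | **yes** | no | no |
| PD, straight to survival follow-up | yes | no | **yes** | no | no |
| Lost to follow-up or left the study at end of treatment | yes | no | **yes** | no | no |
| Entered tumour follow-up, ongoing | yes | no | yes | yes | yes |
| Entered tumour follow-up, ended | yes | yes | no | no | no |

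The rule as written misclassifies three of the six routes. With the entry condition, all six are right.

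**Step 2. Row arithmetic**

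Let T be the number with an End of Treatment page, P the number with an End of Post Treatment page, and E the number who entered the phase.

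- As written: still in = T − P; discontinued from post-treatment follow-up = P; sum = T.
- The sum should be E. The excess is T − E, exactly the discontinued patients who never entered.
- With the entry condition: still in = E − P, and the sum is E.

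**Step 3. Scale**

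- Amendment 6 rationale: 42 + 40 + 12 + 44 + 18 = 156 enrolled at 11 April 2018, and 45 still receiving ceritinib.
- Off treatment: 156 − 45 = 111, taking all enrolled patients as treated.
- Wrongly counted = s × 111, where s is the share of these who never entered tumour follow-up. The documents do not give s, so the range is 0 to 111. For orientation only, an assumed s of 50% gives 0.5 × 111 ≈ 56, and 90% gives 0.9 × 111 ≈ 100.

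The SAP is written for the final study report (SAP 1). The Amendment 6 rationale ends the study once ongoing patients have moved to the rollover study or another source of ceritinib, or have stopped. If every treated patient then has an End of Treatment page, T is the whole FAS. The true number still in tumour follow-up should be at or near zero, while the row would still hold everyone who skipped the phase.

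**The case against.** **The sub-heading.** The row sits under a sub-heading about the post-treatment phase, so a programmer might apply it only to patients who entered. That may well be the intention, but the derivation is explicit and omits the restriction. The other rows under that sub-heading restrict themselves by requiring the second page; this one is defined by its absence.

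**Who files the second page.** The eCRF logic is not in the documents, and Protocol Appendix 2 (14.2.31) lists death and progression among the study phase completion reasons. But it places that visit after post-treatment evaluations and does not ask for it from patients who had none. If sites did file the page for everyone, the surplus would move to the discontinued row; by Step 2 the two rows would still sum to T and not to E.

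**Follow-up is reported elsewhere.** This stands. The SAP summarises duration of follow-up for PFS and OS, and censoring reasons for both. The disposition table also gives a correct count of those who entered the phase. This limits the harm.

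**Stronger readings that the documents do not support**

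- A reader might infer that a patient followed only for survival is counted in both rows for discontinuation from the study. The post-treatment row requires a completed End of Post Treatment page and no survival follow-up, so such a patient fails it. Whether the treatment-phase row catches that patient depends on whether the eCRF treats survival follow-up as a next phase, which is not shown.
- A reader might assume that 60 to 80% of the 111 skipped the phase and report 67 to 89 patients as mislabelled. No document gives that share, and the 2018 snapshot is not the final table.
- A reader might count all withdrawals among the mislabelled. Withdrawal from assessments alone leads to survival follow-up (Protocol 7.1.6.3), and stopping ceritinib by patient or physician decision is not a reason that excludes tumour follow-up under 7.1.6.2.

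**Conclusion.** The point holds for this one row: a stated derivation gives a wrong count for any patient who has an End of Treatment page and never entered post-treatment tumour follow-up. It rests on one assumption, that such patients file no End of Post Treatment page, which Protocol 7.1.4.1 and 7.1.6.2 and the SAP's own direct-route rows support. Without that assumption the failure to reconcile in Step 2 remains, but in the other row.

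The number affected cannot be determined. The available anchor is 111 of 156 patients off treatment at Amendment 6, with an unknown share having skipped the phase. The consequence is a misleading disposition table. No efficacy or safety endpoint is derived from the row, so ORR, DCR, PFS and OS are unaffected.

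**What to change.** In SAP 2.5, define the row as: End of Treatment page present, *Next Phase Entered* on that page equal to *Post-treatment follow-up*, and no End of Post Treatment page.

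Add a programming check that entered = still in + discontinued from post-treatment follow-up. If it fails because some patients who never entered have the second page, apply the same entry condition to the discontinued row. Requiring all rows to sum to the FAS would not work, because they are nested: patients who discontinued treatment include those who entered each later phase.

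The cost is one added condition in the SAP and its program, plus the check. The field is already used for the row that counts entry, so no new data are needed.
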